9.7 Analysis of Correlative Endpoints

9.7.1 Relationship Between *IDH1/2* Mutational Status and Response to Study Treatment

We will compare the difference in the objective response rate among patients with *IDH1/2* mutations as compared those without *IDH1/2* mutations using Fisher's exact test.

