1.3 Correlative Objectives

- 1.3.1 To determine the *IDH1/2* mutational status of subject's tumors and to evaluate for a relationship between presence of *IDH1/2* mutation and clinical benefit from study treatment.
- 1.3.2 To conduct RNAseq analysis using baseline and on-treatment tissue biopsies to study the effects of study treatment on CS gene expression patterns and identify candidate genes which may underlie treatment efficacy.
- 1.3.3 To evaluate for changes in global DNA methylation levels using baseline and on-treatment biopsies and correlate changes in global methylation with clinical benefit from study treatment.
- 1.3.4 To use multiplex immunohistochemistry to interrogate the immune microenvironment in baseline and on-treatment tissue biopsies to define changes in infiltrating immune cell subsets and PD-L1/MHC expression by immune and tumor cells associated with study treatment.

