5.7 Biomarker Plan

List of Biomarker Assays in Order of Priority

Priority	Biomarker Name	Assay (CLIA: Y/N)	Use in the Trial and Purpose	Specimens Tested	Collection Time Points	Mandatory or Optional	Assay Laboratory and Lab PI
Tissue-based Biomarkers							
1	Whole Exome Sequencing in Tumor Tissue	WES CLIA: N	Integrated To evaluate the genomic landscape of chondrosarcoma tumors, including IDH1/2 mutational status. To evaluate whether IDH1/2 mutational status is related to clinical benefit from study treatment.	DNA from FFPE tumor tissue	Pre-treatment (within 21 days of C1D1) Cycle 2 Day 3, 4, or 5 (2-8 hours post dose)	M	Molecular Characterization (MoCha) Laboratory, Frederick National Laboratory for Cancer Research (FNLCR) [name].
2	RNAseq	RNAseq CLIA: N	Integrated To evaluate for changes in gene expression associated with study treatment to interrogate the mechanism of action. Specific hypotheses will be tested based upon the preclinical data.	RNA from FFPE tumor tissue	Pre-treatment (within 21 days of C1D1) Cycle 2 Day 3, 4, or 5 (2-8 hours post dose)	M	Molecular Characterization (MoCha) Laboratory, Frederick National Laboratory for Cancer Research (FNLCR) [name].

Priority	Biomarker Name	Assay (CLIA: Y/N)	Use in the Trial and Purpose	Specimens Tested	Collection Time Points	Mandatory or Optional	Assay Laboratory and Lab PI
Tissue-based Biomarkers							
3	Tumor Immune Microenvironment	Multiplex IHC using the VECTRA and inFORM platforms CLIA: N	Exploratory To evaluate effects of study treatment on the immune microenvironment using multiplex immunohistochemistry to define changes in infiltrating immune cell subsets and expression of PD-L1 and MHC by tumor and immune cells.	Unstained slides from FFPE tumor tissue core	N/A (Collected as part of the WES/ RNAseq biopsies)	O	Columbia University Medical Center Immune Monitoring Core [name]. [contact]
Blood-based Biomarkers							
1	Companion Germline Sequencing	CLIA: N	Integrated To collect a blood sample for germline WES to complement the tumor tissue WES.	DNA from Blood in EDTA	Pre-treatment (within 21 days of C1D1)	M	Molecular Characterization (MoCha) Laboratory, Frederick National Laboratory for Cancer Research (FNLCR) [name].

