9.1 Study Design/Endpoints

9.1.1 Primary Endpoint

The primary endpoint for this phase 2 study is the objective response rate. Noting that chemotherapy is associated with objective response rates of 8-12% in conventional chondrosarcoma (Fox *et al.*, 2012; Italiano *et al.*, 2013), and most clinical trials with targeted agents have shown response rates of 0%, we will consider an objective response rate of 8% as reflecting the activity of chemotherapy and an objective response rate of 28% suggesting promising activity warranting further study. A Simon optimal 2 stage design is employed. The design calls for 26 patients. In stage one, 13 patients will be enrolled. If 2 or more responses are observed, the study will proceed to full accrual. If 5 or more responses are seen among the 26 patients, the study treatment is considered promising for further study. This design has 85% power with alpha of 0.054 to test for a response rate of 8% (null hypothesis) *versus* 28% (alternative hypothesis). The probability of early stopping is 72%.

With Amendment 5, the study was modified to substitute AST727 for SGI-110 (guadecitabine). At that time, 6 patients had been enrolled and initiated study treatment. We will report safety and efficacy separately for these 6 patients. We will report the objective response rate, progression-free survival and safety and tolerability for this group of patients. These 6 patients will be replaced. The Simon optimal 2 stage design described above will be applied to patients receiving the belinostat and ASTX727 combination.

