9.7.3 Changes in Global DNA Methylation

A Wilcoxon signed-rank test with continuity correction will be used to calculate P values for comparing methylation level distribution at the different time points.

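### Section 9.7.3 relates methylation change to no outcome, so objective 1.3.3 has no stated analysis; Section 9.7.1 narrows the IDH1/2 clinical-benefit objective to response alone, with low precision

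*Combined protocol and SAP*

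**What the plan says.** Two correlative objectives in Section 1.3 concern outcome. Objective 1.3.1 looks for a relationship between presence of an IDH1/2 "mutation and clinical benefit from study treatment". Objective 1.3.3 undertakes to "correlate changes in global methylation with clinical benefit from study treatment". The biomarker plan (Section 5.7) classes tumour exome sequencing as integrated and gives as one purpose to learn whether IDH1/2 "mutational status is related to clinical benefit from study treatment". Clinical benefit is not defined in any of these places.

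The matching analyses are one sentence each:

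- Section 9.7.1: "We will compare the difference in the objective response rate among patients with" IDH1/2 mutations and those without, using Fisher's exact test.
- Section 9.7.3: a Wilcoxon signed-rank test "will be used to calculate P values for comparing methylation level distribution at the different time points".

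Section 9.6.2 plans Kaplan-Meier PFS for the cohort as a whole, with no breakdown by biomarker. Section 9.7 gives no significance level, effect size, power or analysis population for either comparison. On size, Section 9.1.1 says "The design calls for 26 patients" and "In stage one, 13 patients will be enrolled". The six SGI-110 patients are outside that design and are reported separately for efficacy and safety.

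**The concern.** A signed-rank test on paired samples shows whether methylation moved under treatment. It cannot show whether patients whose methylation moved more did better, which is what objective 1.3.3 asks. Section 2.4.2.2 proposes methylation as a possible biomarker of anti-cancer effect, and the paired samples come from mandatory research biopsies (Section 5.1) that Section 5.2 describes as having no clinical impact for the patient.

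For IDH status the gap is narrower. Response is one form of benefit and it is analysed. But PFS, a secondary endpoint, is never examined by IDH status, and the one planned test rests on a handful of responders. With clinical benefit undefined, the measure could be chosen after the data are seen.

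**Working it through.** **1. Objectives against analyses.**

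| Objective | Asks for | Section 9.7 provides | Gap |
|---|---|---|---|
| 1.3.1 | IDH1/2 status vs clinical benefit | Response by IDH status, Fisher's exact test | PFS and tumour shrinkage not examined; benefit undefined |
| 1.3.3 | Methylation change vs clinical benefit | Methylation, baseline vs on-treatment | No outcome variable |

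**2. The only power the plan states.** This is for the primary endpoint: 13 then 26 patients, continue with at least 2 responses, promising with at least 5. Power is the sum over x = 2 to 13 of P(X1 = x) × P(X2 ≥ 5 − x), where X1 and X2 are each binomial(13, p). At p = 28% this gives 0.851, against 85% stated. The probability of at most 1 response in 13 at p = 8% is 0.721, against 72% stated. The same rule at 8% gives a type I error of 0.045, not the stated 0.054; that is a separate matter and does not affect this point. No power is stated for 9.7.1 or 9.7.3.

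**3. Precision of the IDH comparison.** Inputs: N = 26 (Section 9.1.1) and mutation prevalence 50-60% (Section 2.1), so 13 to 16 mutant and 13 to 10 wild-type patients. Assumptions: two-sided 0.05 and the response rates shown. The 28% and 8% are borrowed from the primary test for scale; the plan does not give them as subgroup rates. Power is the sum, over all tables with Fisher p ≤ 0.05, of the product of the two binomial probabilities.

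| Mutant/wild type | 28% vs 8% | 35% vs 5% | 50% vs 8% |
|---|---|---|---|
| 13/13 | 11.6% | 31% | 55% |
| 14/12 | 15.6% | 38% | 61% |
| 15/11 | 10.2% | 29% | 56% |
| 16/10 | 6.4% | 21% | 50% |

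If wild-type patients are the better responders (8% vs 28%), the range is 12-20%. At 14/12, 80% power needs about 61% versus 8%. If the trial stops at 13 patients (7/6 split), power for 28% versus 8% is about 1%.

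**4. What five responders can show.** Five is the plan's threshold for promising activity. At 14/12, all five in mutants has probability C(14,5)/C(26,5) = 2002/65780 = 0.0304. Adding the more extreme opposite table, C(12,5)/C(26,5) = 792/65780 = 0.0120, gives p = 0.042. A 4-1 split gives p = 0.33. All five in mutants gives p = 0.053 at 15/11 and 0.12 at 16/10.

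**5. What the added analyses could show.**

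- PFS by IDH status, 14/12, assumed hazard ratio 0.5, all 26 patients with an event: power = Φ(√(26 × 14/26 × 12/26) × ln 2 − 1.96) = Φ(2.542 × 0.693 − 1.96) = Φ(−0.20) = 42%. Eighty percent power would need 66 events.
- Methylation change in 7 responders versus 19 non-responders (28% of 26 is about 7), all 26 pairs available: power is 44% at a standardised difference of 0.8 and 81% at 1.25.
- Rank test on best percent change by IDH status, simulated at 14/12. If every mutant tumour shifts equally on a normal scale, power is about 48% (28% vs 8%) and 84% (35% vs 5%). If IDH status changes only the fraction who respond (responders uniform from −60 to −30, non-responders about normal with mean 5 and SD 15), it is about 13-14% and 24-25%, below Fisher's 16% and 38%.

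**The case against.** These are correlative objectives in a 26-patient single-arm trial. The plan claims no power for them, and low precision is to be expected. Response is the primary endpoint and a fair component of benefit, so 9.7.1 does bear on objective 1.3.1. For objective 1.3.3 the paired biopsies and the outcomes are already planned, so a sentence is missing, not data. The added comparisons would be imprecise too, and best percent change is not a protocol endpoint: patients who die early or are not assessable may have no follow-up sum of diameters, yet they count as failures in the response analysis.

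All of that stands, and it limits the point. It does not supply the missing link in 9.7.3 or a definition of clinical benefit.

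A reader might go further and infer that neither question can be answered, or that the Fisher test will almost surely find nothing. The documents do not support that: 9.7.1 yields an estimate for response, and power reaches 50-61% for 50% versus 8%. Nor is any single power figure a property of the plan, since each depends on an assumed split and assumed rates. A reader might also infer that the trial's mechanism goes untested. Sections 9.7.2 to 9.7.4 examine expression, methylation and immune changes, and Section 2.3.1 reports preclinical efficacy irrespective of IDH status.

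**Conclusion.** The mismatch holds on the text. Section 9.7.3 does not address objective 1.3.3, and Section 9.7.1 addresses objective 1.3.1 for response only, leaving clinical benefit undefined. The planned Fisher test is imprecise: about 6-16% power for an assumed 28% versus 8% with mutants higher, and about 50-61% for an assumed 50% versus 8%, over splits from 13/13 to 16/10 and a two-sided 0.05 level. A non-significant result would therefore say little about a moderate IDH effect.

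Replacing Fisher's test with a rank test on best percent change might look like the remedy. That is not supported: the gain appears under a uniform normal shift and reverses when only the responding fraction differs. Best percent change belongs as a supplement. This is a minor point about correlative aims and does not touch the primary analysis. Parts of Section 5.8 were missing from the text available, so correlative detail there could not be checked; Section 9.7 was available.

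**What to change.** - **Definition.** State in Section 1.3 or 9.7 which measures count as clinical benefit, for example response, PFS and best percent change in the sum of target diameters.
- **Population.** State that the correlative analyses use the ASTX727 patients, with the six SGI-110 patients shown separately, as for the other endpoints.
- **Section 9.7.3.** Keep the signed-rank test. Add an association of methylation change with outcome in patients with paired biopsies: a rank correlation with best percent change (patients with a follow-up scan) and a comparison by response or PFS.
- **Section 9.7.1.** Keep the response table and report the difference in response rates with a confidence interval. Add Kaplan-Meier PFS by IDH status and, as a supplement, best percent change by IDH status, giving the number of patients without a follow-up scan.
- **Labelling.** Call all of this exploratory, report estimates with confidence intervals, and claim no power gain over Fisher's test.

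The cost is a few lines of text, with no new visits, assays or patients. The downside is a few more exploratory comparisons of low precision.

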9.7.2 Changes in Expression of CS genes and Candidate Genes Affecting Gene Efficacy

Data from RNAseq will be analyzed in collaboration with the MoCha lab, differential expression profiles between baseline and on-treatment samples will be analyzed at the gene level and gene

expression changes defined as significant based on absolute \log_2 fold changes >2 and adjusted p values <0.005 for each comparison with consideration of the false discovery rate.

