2.4.2 Exploratory Studies

2.4.2.1 Tumor Immune Microenvironment

The effectiveness of many anti-cancer therapeutics depends upon activity of the immune system. Many cancers alter normal cellular processes to evade immune surveillance, and increasing evidence suggests that immune evasion is accomplished in part through epigenetic modification of genes involved in antigen presentation, expression of immunosuppressive cell surface molecules, suppression of candidate neoantigens, and other mechanisms. There is increasing evidence to support combining epigenetic-based therapies, including HDAC and DNMT inhibitors, with immune checkpoint inhibitors, and clinical trials with these combinations are ongoing (Weisenberger *et al.*, 2006). However, studies evaluating the effects of epigenetic treatments on the immune microenvironment using tissue from prospective clinical trials with HDAC and DNMT inhibitors is limited. We will analyze changes in densities of infiltrating immune cell subsets between pre-treatment and on-treatment specimens to evaluate changes induced by study treatment. We hypothesize that belinostat and SGI-110 (guadecitabine) or ASTX727 treatment will induce expression of MHC and PD-L1 by tumor cells and will increase infiltration of cytotoxic T-cells into chondrosarcoma tumors.

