5.2 Summary Tables for Interventional Radiologist for Research Biopsies

Biopsy #: 1
Trial Time Point: Pretreatment (within 21 days of C1D1)
IR Biopsy Definition: Research – No Clinical Impact (All cores from a single biopsy procedure impact research goals, but do not directly impact patient care or benefit the patient.)

Core Priority	Use in the Trial	Biomarker Name(s)	Tumor Content Required	Post-Biopsy Processing
1	Integrated	WES/RNAseq in Tumor Tissue	>50%	formalin
2	Exploratory	Global Methylation Assay	>50%	formalin
3	Exploratory	Tumor Immune Microenvironment	>50%	formalin

Biopsy #: 2				
Trial Time Point: Cycle 2, Day 3, 4, or 5 (2-8 hours post treatment)				
IR Biopsy Definition: Research – No Clinical Impact (All cores from a single biopsy procedure impact research goals, but do not directly impact patient care or benefit the patient.)				
Core Priority	Use in the Trial	Biomarker Name(s)	Tumor Content Required	Post-Biopsy Processing
1	Integrated	WES/RNAseq in Tumor Tissue	>50%	formalin
2	Exploratory	Global Methylation Assay	>50%	formalin
3	Exploratory	Tumor Immune Microenvironment	>50%	formalin

Note: Pre-biopsy assessments will be reported and tracked through a trial-specific CRF within the CTEP Medidata Rave system (see Appendix C).

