5.8 Integrated Correlative Studies

5.8.1 Whole Exome Sequencing in Tumor Tissue

5.8.1.1 Specimen Receipt and Processing at the EET Biobank

Tumor tissue received in formalin will be paraffin-embedded. All FFPE blocks will be sectioned to generate an initial hematoxylin and eosin (H&E)-stained slide and, for nucleic acid extractions, additional RNase-free slides. If needed, slides will be macrodissected to enrich tumor content before scraping for nucleic acid co-extraction.

DNA and RNA will be co-extracted from tumor tissue. The nucleic acids will be analyzed to determine concentration and quality. Aliquots of DNA will be shipped to the central sequencing laboratory for analysis.

DNA will be extracted from whole blood in EDTA. An aliquot of blood (germline) DNA will be shipped with the tumor DNA.

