5.8.2 RNAseq

5.8.2.1 Specimen Receipt and Processing at the ETCTN Biorepository

Tumor tissue received in formalin will be paraffin-embedded. All FFPE blocks will be sectioned to generate an initial hematoxylin and eosin (H&E)-stained slide and, for nucleic acid extractions, additional RNase-free slides. If needed, slides will be macrodissected to enrich tumor content before scraping for nucleic acid co-extraction.

DNA and RNA will be co-extracted from tumor tissue. The nucleic acids will be analyzed to determine concentration and quality. Aliquots of RNA will be shipped to the central sequencing laboratory for analysis.

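### The global methylation comparison has no tumour-content term, so a systematic fall in tumour content on treatment could pass for demethylation; the same risk for RNAseq is narrow

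*Combined protocol and SAP*

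**What the plan says.** Objectives 1.3.2 and 1.3.3 ask what treatment does to chondrosarcoma gene expression and global DNA methylation, using paired baseline and on-treatment biopsies.

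- **Methylation (9.7.3):** "A Wilcoxon signed-rank test with continuity correction will be used to calculate P values for comparing methylation level distribution" between time points. No covariate, minimum effect size or significance level is given.
- **RNAseq (9.7.2):** "differential expression profiles between baseline and on-treatment samples will be analyzed at the gene level". A gene counts as changed on absolute log2 "fold changes >2 and adjusted p values <0.005 for each comparison with consideration of the false discovery rate". No covariate is named.
- **Specimens (5.2):** the column "Tumor Content Required" reads >50% for the WES/RNAseq core and the methylation core, at both biopsies.
- **Processing:** for nucleic acids, "If needed, slides will be macrodissected to enrich tumor content before scraping for nucleic acid co-extraction" (5.8.2.1, and likewise 5.8.1.1). No target content is set and the two time points are not matched. Section 5.9.2.1 sends unstained slides to the methylation laboratory and states no macrodissection.
- **Expected biology:** Section 2.4.2.1 hypothesises that treatment "will increase infiltration of cytotoxic T-cells into chondrosarcoma tumors". Section 2.3.1 says IDH1/2 mutation, present in 50-60% of conventional cases, causes global hypermethylation.
- **Data that could measure cell mix:** "All FFPE blocks will be sectioned to generate an initial hematoxylin and eosin (H&E)-stained slide" (5.8.1.1, repeated for the methylation blocks in 5.9.2.1). WES is planned at both time points with matched germline (5.7). Multiplex IHC of immune subsets, PD-L1 and MHC is compared between biopsies (9.7.4). None of these is linked to the methylation or RNAseq analysis.

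**The concern.** A bulk value is a weighted average over tumour and non-tumour cells. With cores anywhere from just over 50% to 100% tumour, the weights can differ widely within a pair. Random differences in content only add noise. A shift in one direction adds bias, and the protocol's own infiltration hypothesis supplies a plausible direction: if T cells enter without an equal gain in tumour cells, tumour content falls. In a hypermethylated tumour that lowers the bulk value, which is the hypothesised drug effect.

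At stake is the interpretation of a pharmacodynamic result. Section 2.4.2.2 proposes the change in methylation as a possible biomarker of the treatment's anti-cancer effect, so a shift in cell mix read as tumour-cell demethylation would mislead later work.

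**Working it through.** The documents give no power or error rate for these analyses, so there is no stated figure to reproduce. The check uses a two-compartment mixture with no change in any cell.

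**Methylation.** Let p1 and p2 be tumour content at the two biopsies, and D be tumour minus non-tumour methylation. Then

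apparent change = (p2 − p1) × D.

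A 10-point fall with D of 10 to 20 points gives an apparent loss of 0.10 × 10 = 1 point to 0.10 × 20 = 2 points.

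From the documents: at most 26 pairs on belinostat and ASTX727, or 13 if accrual stops at stage 1 (9.1.1). Assumed, because the documents are silent: mean fall 5 or 10 points; SD of content change 12 points; D of 10-20 points; assay SD 2 points on the paired difference; two-sided 5% level. The SD of the paired difference is then

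- D = 10: √[(0.12 × 10)² + 2²] = √5.44 = 2.33 points
- D = 20: √[(0.12 × 20)² + 2²] = √9.76 = 3.12 points.

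For a 10-point fall and 26 pairs, the mean over its standard error is (1/2.33) × √26 ≈ 2.2 and (2/3.12) × √26 ≈ 3.3, so frequent rejection is expected. Simulated signed-rank rejection rates with no drug effect:

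| Pairs | Mean fall | All tumours carry D | 55% carry D, the rest none |
|---|---|---|---|
| 26 | 10 points | 53-86% | 19-40% |
| 26 | 5 points | 18-34% | 8-14% |
| 13 | 10 points | 23-50% | 10-18% |
| 26 or 13 | none | about 5% or below | about 5% or below |

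The 55% is the midpoint of the protocol's 50-60% IDH mutation range; zero contrast in the remainder is an assumption.

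Sensitivity, all tumours carrying D, 10-point fall, 26 pairs:
- Baseline content 80% and content SD 10 points at each biopsy: 48% (D = 10) and 78% (D = 20).
- Assay SD 2 points per measurement instead of per difference: 33-71%.

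Regressing the paired methylation change on the change in tumour content (measured with SD 5 points) and testing the intercept rejects in about 4-9% of trials.

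**RNAseq.** With R the non-tumour to tumour expression ratio,

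fold change = [p2 + (1 − p2)R] / [p1 + (1 − p1)R].

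- Gene expressed only in tumour: at most a halving (100% to 50%), so |log2| ≤ 1. It never crosses 2.
- Gene expressed only outside tumour: fold = (1 − p2)/(1 − p1). A 10-point fall gives 0.15/0.05 = 3 (log2 1.58) from 95%, 0.20/0.10 = 2 (1.00) from 90%, and 0.30/0.20 = 1.5 (0.58) from 80%. None crosses. For a 10-point fall to cross, baseline non-tumour content q must satisfy (q + 0.10)/q > 4, so q < 3.3%.
- With the largest permitted fall, to 50%, crossing still needs baseline non-tumour content below 0.50/4 = 12.5%. From 90% to 55% gives 0.45/0.10 = 4.5 (log2 2.17).
- Gene expressed in both: from 95% to 55% it crosses only if R is at least 13; from 90% to 55%, at least 61.
- An immune subset rising from 1% to 5% at fixed tumour content gives a 5-fold change (log2 2.32). A purity covariate would not remove this.

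**The case against.** A reader might infer that false findings of demethylation and gene induction are likely, or that the plan cannot separate tumour reprogramming from a change in cell mix. The documents do not support that.

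- The mean fall in content, the methylation contrast and the SDs appear nowhere in the documents. The infiltration hypothesis carries no size, and without a systematic fall the test keeps its level. This stands: the methylation risk is conditional.
- Hypermethylation is tied to IDH mutation in 50-60% of cases, so applying the contrast to every patient overstates the bias. This stands, and is why the table has a second column.
- The fourfold RNAseq rule stops artefacts for tumour-expressed genes and for moderate falls in content. This stands. Only genes expressed mainly outside the tumour, with very pure baseline cores or a rise in a rare subset, remain exposed.
- Multiplex IHC measures PD-L1 and MHC on tumour and immune cells at both biopsies. This stands, although 9.7 does not link it to the RNAseq results.
- Infiltration is itself a hypothesised effect (2.4.1.2, 2.4.2.1), so adjusting for purity changes the RNAseq question. This stands as a reason not to make the adjusted RNAseq model the main one.
- Macrodissection, or analysis detail settled with the sequencing laboratory, may cover the gap. This stands only in part. Macrodissection is conditional, has no target, is not stated for the methylation slides and cannot remove intermingled cells. Section 9.7 names no adjustment.

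**Conclusion.** The omission is real and matters most in 9.7.3, which has no effect-size threshold and no stated enrichment of the methylation slides. If tumour content falls by 10 points on average, the signed-rank test with 26 pairs would report a change in about 53-86% of trials with no drug effect when all tumours are hypermethylated, and in about 19-40% when 55% are. These figures rest on the assumed contrast, fall and SDs. The size varies across the input sets tried, but in each a 10-point mean fall took rejection well above 5%.

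For 9.7.2 the concern is limited to genes expressed mainly in non-tumour cells. That class still matters because interferon-related genes, MHC and PD-L1 feature in the protocol's hypotheses and infiltrating cells can contribute to their bulk signal. A broader claim of general RNAseq bias fails on the arithmetic above.

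Both endpoints are correlative and the methylation assay is exploratory. No eligibility, stopping or response decision depends on them. This is a cheap improvement in how the results can be interpreted.

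**What to change.** **Section 9.7.3.** Record the tumour-cell fraction of each methylation core from its existing H&E slide. Pre-specify a regression of paired methylation change on change in tumour-cell fraction, with a test of the intercept, reported beside the signed-rank test. State that a claim of tumour demethylation needs support from the adjusted result.

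**Section 9.7.2.** Keep the unadjusted paired comparison as the main analysis. Add a sensitivity analysis with tumour purity as a covariate, estimated from the WES already planned at both time points. State that changes in interferon, MHC and PD-L1 genes will be read against the multiplex IHC, since a purity covariate does not correct for shifts within the non-tumour cells.

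**Cost.** Analysis-plan wording, a pathologist's reading of slides already cut, and a little bioinformatics; no new samples or assays. The adjusted analysis spends one degree of freedom among at most 26 pairs and loses some precision through error in measured tumour content.
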